infusion or at high versus low dose during a hospitalization for ADHF, with high dose therapy currently considered as usual care by most clinicians.²⁴ Importantly, there are several reasons why loop diuretics might be less effective or even harmful in CHF. First, loop diuretics directly stimulate renin production by inhibiting the $\text{Na}^+/\text{K}^+/\text{2Cl}^-$ -cotransporter on the luminal side of the macula densa, which depletes intracellular chloride levels in the macula densa. The consequence is an increased COX-2 and NOS I activity in macula densa cells, leading to paracrine PGE_2 and NO secretion.²⁵ Both PGE_2 and NO work in concert to stimulate renin release by granulosa cells of the afferent arteriole and further detrimental activation of the renin-angiotensin-aldosterone axis. Second, impaired secretion of loop diuretics in the proximal tubules of CHF patients, especially when there is concomitant renal dysfunction, results in lower concentrations at the place where these agents act – the luminal side of the thick ascending limb of Henle’s loop (TAL). Third, increased sodium reabsorption in the proximal tubules might result in less sodium offered to the TAL, especially if glomerular filtration is concomitantly impaired, hampering the efficacy of loop diuretics. As a result, physicians often use combination therapies of different acting diuretic agents in order to increase the overall diuretic effect.

From a pathophysiological point of view, targeting sodium reabsorption in the proximal tubules has several potential benefits in CHF. First, it is the place where most sodium is reabsorbed, especially in ADHF. Second, greater delivery of chloride to macula densa cells will decrease renin production, ceasing neurohumoral activation. Third, endogenous natriuretic peptides (acting in the distal nephron) will possibly regain their effects. The carbonic anhydrase inhibitor acetazolamide (Diamox®), which is approved for the treatment of mountain sickness and is used to increase the diuretic efficacy of loop diuretics in patients with therapy-refractory congestion, inhibits sodium reabsorption in the proximal tubules. Remarkably, in a small study of 9 patients with advanced CHF and diuretic resistance, therapy with acetazolamide was able to elicit potent diuresis.²⁶ Despite this

promising case series and the pathophysiological rationale for inhibition of proximal sodium reabsorption in ADHF, acetazolamide is now a largely forgotten diuretic.

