MRA have an established role in the treatment of chronic CHF.^{11, 12} However there are remarkable few data on their use in patients who present with ADHF. Nevertheless, in this context with frequent use of potassium wasting diuretics, they might be of particular interest to prevent occurrence of hypokalemia, which has been associated with a worse prognosis.²⁷ Moreover, by inhibiting distal tubular sodium reabsorption and counteracting aldosterone breakthrough, MRA might improve the natriuretic efficiency of loop diuretics.

2. Study Hypotheses

1. Combination therapy with acetazolamide improves loop diuretic efficacy to induce natriuresis in ADHF patients, allowing for a lower dose of the latter medication and potentially less adverse events such as worsening renal function.
2. Combination therapy with acetazolamide and low-dose loop diuretics leads to less pronounced neurohumoral activation compared to treatment with high-dose loop diuretics in ADHF patients.
3. Upfront therapy with MRA is safe in patients presenting with ADHF and lowers the incidence of hypokalemia and the need for potassium supplementation, without causing a higher incidence of hyperkalemia.
4. Combination diuretic therapy with acetazolamide and/or upfront spironolactone will lead to improved clinical outcome (less heart failure rehospitalizations and lower all-cause mortality).

3. Study Protocol

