3.4. Collected data

- Baseline at the moment of randomization
 - Demographics, medical history, current medical therapy, baseline body weight, blood pressure, heart rhythm (sinus or not), heart rate, Visual-analogue scale (VAS) score for dyspnea and 4-point Likert scale for edema will be assessed upon study inclusion
 - Blood sample: hematocrit, electrolytes, serum osmolality, serum urea, serum creatinine, serum Cystatin C, serum urate, plasma renin activity (PRA), plasma aldosterone, plasma adrenaline, plasma noradrenaline, total protein, plasma NT-proBNP
- Day 1-3:
 - VAS score for dyspnea
 - 4-point Likert scale for edema
 - Body weight and fluid balance
 - Blood pressure, heart rate, heart rhythm
 - Blood sample: hematocrit, electrolytes, serum osmolality, serum urea, serum creatinine, serum Cystatin C, serum urate, PRA, plasma aldosterone, plasma adrenaline, plasma noradrenaline, total protein, plasma NT-proBNP
- Three consecutive 24h urinary collections will be performed; the first one started with the first bolus administration of loop diuretics; urinary assessment of creatinine, protein, sodium, potassium, chloride, ureum, urate, microalbuminuria
- At an outpatient follow-up appointment 2-6 weeks after hospital discharge, a final blood sample with hematocrit, electrolytes, serum osmolality serum urea, serum creatinine, serum Cystatin C, serum urate and plasma NT-proBNP will be collected.
- All-cause mortality and hospital readmissions will be collected prospectively for the study cohort. The patient will receive a telephone call from a study nurse after 3, 6, 9 and 12 months

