3.5.3. Secondary end-points

- Relative plasma NT-proBNP change (%) after 72 h compared to admission
- Worsening renal function defined as a >0.3 mg/dL increase in serum creatinine or a >20% decrease in estimated glomerular filtration rate by the CKD-EPI formula compared to baseline at any time point before 72 h
- Persistent renal impairment, defined as persistently elevated serum creatinine levels >0.3 mg/dL or a >20% decrease in estimated glomerular filtration rate by the CKD-EPI formula compared to baseline at the moment of outpatient follow-up 2-6 weeks after hospital discharge.
- Peak plasma aldosterone concentration (ng/L) after 72 h
- Peak plasma renin activity (ng/mL/h) after 72 h

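### The two peak end-points for renin activity and aldosterone leave open whether the randomization sample counts, and the planned comparison makes no use of the baseline values collected

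*Combined protocol and SAP*

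**What the plan says.** Section 3.5.3 lists "Peak plasma aldosterone concentration (ng/L) after 72 h" and "Peak plasma renin activity (ng/mL/h) after 72 h" among the secondary end-points, and adds nothing on how either is derived.

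Section 3.4 places both assays in the randomization sample ("serum urate, plasma renin activity (PRA), plasma aldosterone, plasma adrenaline, plasma noradrenaline") and again under Day 1-3 ("serum Cystatin C, serum urate, PRA, plasma aldosterone, plasma adrenaline, plasma noradrenaline, total protein, plasma NT-proBNP"). The outpatient sample at 2-6 weeks does not include them. The number of draws per day and their clock time are not given; one per day is the natural reading.

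Hypothesis 2 in section 2 is comparative: acetazolamide with low-dose loop diuretics "leads to less pronounced neurohumoral activation compared to treatment with high-dose loop diuretics in ADHF patients". The background gives both arms a direction. For proximal inhibition, "greater delivery of chloride to macula densa cells will decrease renin production, ceasing neurohumoral activation"; for the comparator, "loop diuretics directly stimulate renin production". Neither effect is given a size.

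Section 3.6 compares groups by Student's t-test or the Mann-Whitney U test, at two-sided 0.05. It contains no baseline adjustment and no rule for missing samples.

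**The concern.** A peak is a maximum over a set of samples, and 72 h is a time point. The wording therefore allows three readings: the maximum with the randomization sample, the maximum without it, or the value at 72 h. The last conflicts with the word peak. Other end-points in 3.5.3 name their reference (admission or baseline), and the spironolactone primary end-point in 3.5.2 names its window. These two do neither.

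The choice matters because the background expects renin to fall under acetazolamide. If the pre-treatment value is in the set, a patient whose renin falls on every day is scored at the untreated level. If the rule is settled after the data are in, it can be settled in favour of a result.

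Separately, each patient brings a pre-treatment renin activity and aldosterone value, and the planned test ignores it.

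**Working it through.** The plan gives no SD, effect size or power for these end-points, so there is no stated figure to reproduce.

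**Inputs from the document.** Four groups of 20 (3.1), hence 40 v 40 for the acetazolamide comparison; two-sided alpha 0.05 (3.6); one baseline and three later values (3.4, one draw per day assumed).

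**Assumptions.** Values at baseline and Days 1-3 are normal (log scale) with SD 1 and equal correlation ρ of 0.5 to 0.9. The treatment effect is the same on each of Days 1-3.

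**Step 1: effect of counting baseline.** Approximate power = Φ(difference / (SD × √(2/40)) − 1.96). For the Day 1-3 maximum at ρ = 0.5, the variance is 0.5 + 0.5 × 0.559 = 0.780 (0.559 is the variance of the largest of three independent standard normals), so SD = 0.883. Then 0.5 / (0.883 × 0.2236) = 2.53, and Φ(2.53 − 1.96) ≈ 0.72. The other entries come from simulation of 400,000 patients, for a 0.5 SD effect:

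| Scenario | ρ | Difference, Day 1-3 only (power) | Difference, baseline counted (power) | Share kept |
|---|---|---|---|---|
| Acetazolamide falls, control flat | 0.5 | 0.50 (0.72) | 0.324 (0.39) | 65% |
| | 0.7 | 0.50 (0.67) | 0.309 (0.32) | 62% |
| | 0.9 | 0.50 (0.63) | 0.257 (0.22) | 51% |
| Control rises, acetazolamide flat | 0.5 | 0.50 (0.72) | 0.414 (0.57) | 83% |
| | 0.7 | 0.50 (0.67) | 0.423 (0.54) | 85% |
| | 0.9 | 0.50 (0.63) | 0.446 (0.53) | 89% |

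Share kept = difference / 0.50. A separate simulation of 4,000 trials at ρ 0.5-0.8 gave 0.29-0.33 SD for the first scenario. With half the effect in each arm, the differences are 0.373, 0.372 and 0.368 (about 74-75% kept).

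**Step 2: within patients.** With baseline in the set, the maximum is at or above baseline by construction. Even after a true fall of 0.8 SD, mean peak minus baseline is +0.26, +0.14 and +0.02 SD at ρ 0.5, 0.7 and 0.9.

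**Step 3: number of samples.** With no change over time, the expected maximum above the mean is 0.564 × √(1 − ρ) for two samples and 0.846 × √(1 − ρ) for three: 0.40 and 0.60 SD at ρ = 0.5, and 0.18 and 0.27 SD at ρ = 0.9. If 30% of one arm only lose Day 3, the bias is 0.3 × (0.597 − 0.399) = 0.06 SD at ρ = 0.5 and 0.3 × (0.268 − 0.179) = 0.03 SD at ρ = 0.9. If they lose Days 2 and 3, it is 0.3 × 0.597 = 0.18 SD and 0.3 × 0.268 = 0.08 SD.

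**Step 4: baseline as covariate.** For the Day 1-3 maximum, a 0.5 SD constant shift and ρ 0.5-0.8, power rises from 64-70% (t-test) to 84-99% (analysis of covariance).

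**Step 5: maximum or mean.** With a constant 0.5 SD shift and ρ 0.5-0.8, t-test power is 64-71% for the Day 1-3 maximum and 66-78% for the Day 1-3 mean. With a 1 SD control-arm rise on one day only, it is 75-84% for the maximum and 34-45% for the mean.

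**The case against.** The strongest defence is that the analysis is between groups and the hypothesis is relative. A fall in one arm still lowers that arm's mean peak even if baseline counts. Where activation rises under high-dose loop diuretics and is blunted by acetazolamide, as the background also suggests, 83-89% of a 0.5 SD contrast survives. This stands. A reader might infer that the end-point cannot show a fall at all; that is true of the individual patient's peak against baseline, but not of the group comparison.

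The defence can add that 3.5.3 names a baseline where it wants one, so leaving it out is the more natural reading here. That is fair, and it makes the attenuation conditional. It does not supply the missing definition.

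A reader might also infer serious bias from unequal sample counts, since 3.3.1 and 3.3.2 allow an early switch of treatment and censoring without saying whether sampling continues. The document does not show unequal loss between arms, and at arm level the bias is small unless several days are lost unevenly (step 3).

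Nor does the evidence support replacing the maximum by a mean. Which is better depends on a time course that the plan does not give (step 5).

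**Conclusion.** The concern holds in a limited form. Both end-points lack a rule on which samples count. If the randomization sample is included, a one-arm fall of 0.5 SD is attenuated to about 0.26-0.33 SD, and power drops to about 22-39% from 63-72%. If it is excluded, that loss does not arise. Under either reading, 3.6 leaves the collected baseline unused, and that costs power: 64-70% against 84-99% in the case examined. These figures rest on assumed SD, correlation (0.5-0.9 for the attenuation, 0.5-0.8 for the covariate gain) and a constant shift over three days; the direction of the findings depends on them less than the size does.

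These are secondary end-points, so the trial's primary conclusions are not touched. They are, however, the only renin-aldosterone end-points for hypothesis 2, and the repair is cheap enough to be worth making.

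**What to change.** - **Section 3.5.3:** define both end-points as the highest post-randomization value among the Day 1-3 samples. State that the randomization sample is not part of the outcome, and how many draws are made per day.
- **Section 3.6:** for these two end-points, compare the groups on the log scale by analysis of covariance, with the log baseline value as covariate. The log of the maximum is the maximum of the logs, so the end-point itself is unchanged.
- **Check on missing samples:** report beside it the mean log Day 1-3 level, or a repeated-measures model that uses whatever Day 1-3 samples exist. The maximum can stay as the named end-point.

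The cost is a few sentences in two sections and one extra model term. Samples and assays stay as planned. Patients without a baseline value would need a stated handling rule, and the mean gives less weight to a single-day spike, so it should stand beside the maximum and not replace it.

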3.5.4. Other pre-specified outcome measures

- Total urinary sodium excretion (mmol) after 48 h and 72 h
- Total urine output after 24 h, 48 h and 72 h
- Change in VAS score for dyspnea at 24 h, 48 h and 72 h
- Change in 4-point Likert scale for edema at 24 h, 48 h and 72 h
- Body weight change upon hospital discharge compared to admission
- Incidence of therapy-refractory congestion defined as the need for combinational diuretic therapy with chlorthalidone, bail-out ultrafiltration or renal replacement therapy

- Incidence of all-cause mortality and readmissions after 1 year

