3.1. Study design

Randomized clinical trial with factorial 2x2 design, 2 treatment arms, and 4 groups (n=20 each):

- Arm 1: Acetazolamide + low-dose loop diuretics versus high-dose loop diuretics (=standard of care)
 - ➔ Triple blinded to treatment allocation (patient, treating physician and investigator blinded)
- Arm 2: Upfront versus discharge spironolactone
 - ➔ Treating physician and investigator blinded to treatment allocation. Patient not blinded to treatment allocation because no matching placebo will be provided due to logistic constraints.

Consecutive patients, presenting with ADHF at different Belgian hospitals will be screened by staff members, cardiology fellows, a study nurse and the cardiology Ph.D. fellows. All those people will be able to login via the website www.hartcentrumlimburg.be, where they can print the case report form and informed consent of the study and will receive the randomization number by a computer algorithm with blocks of 4.

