3.2. Study population

3.2.1. Inclusion criteria

- Older than 18 years of age and able to give informed consent
- Clinical diagnosis of ADHF within the previous 8 h
- At least two clinical signs of congestion (e.g. edema, ascites, jugular venous distension or pulmonary vascular congestion on chest radiography)
- Maintenance therapy with oral loop diuretics at a dose of at least 1 mg bumetanide or an equivalent dose for at least 1 month before hospital admission
Conversion: 1 mg bumetanide = 40 mg furosemide = 20 mg torsemide
- Plasma NT-proBNP >1,000 pg/mL
- Left ventricular ejection fraction <50% (on examination ≤3 months)
- One out of three of the following criteria:
 - Serum sodium <136 meq/L

- Urea/creatinine ratio >50
- WRF defined as a >0.3 mg/dL increase in Cr compared to a previous value within 3 months before admission

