3.6. Statistical analysis

Continuous variables will be expressed as mean \pm standard deviation when normally distributed and as median (interquartile range) in case of a non-normal distribution. Normality will be assessed by the Shapiro-Wilk statistic. The independent-samples Student's *t*-test and Mann-Whitney *U* test will be used as indicated to compare between groups. Categorical variables will be expressed as percentages and compared using Fisher's exact test or Pearson's χ^2 -test in case of a non-binary response. Statistical significance will always be set at a 2-tailed probability level of <0.05 . All statistics will be performed using IBM SPSS® (Chicago, Illinois, USA) (version 22.0 for Mac).

4. Potential adverse events

- Metabolic acidosis is the only agent-specific adverse event that might be expected from treatment with acetazolamide. Serum bicarbonate is monitored daily. If serum bicarbonate <22 meq/L, substitution with oral NaHCO_3 will be provided.
- Hyperkalemia might be expected as a potential adverse event of spironolactone, but this medication will be withheld when serum potassium levels are >5.0 mmol/L and serum potassium levels are monitored daily throughout the study.

5. References

- american heart association. *Circulation*. 2013;127:e6-e245
2. Effect of enalapril on survival in patients with reduced left ventricular ejection fractions and congestive heart failure. The solvd investigators. *The New England journal of medicine*. 1991;325:293-302

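### The edema change score has a probable floor: entry does not require edema and the planned test ignores the baseline score, so this lower-tier outcome loses power, by an unknown amount and without bias.

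*Combined protocol and SAP*

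**What the plan says.** The combined protocol and SAP deals with edema in four places.

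- **Entry (3.2.1).** The congestion criterion is "At least two clinical signs of congestion (e.g. edema, ascites, jugular venous distension or pulmonary vascular congestion on chest radiography"). Edema is one example of four. No other inclusion or exclusion criterion asks for it.
- **Collection (3.4).** At baseline, "Visual-analogue scale (VAS) score for dyspnea and 4-point Likert scale for edema will be assessed upon study inclusion". The score is repeated on days 1 to 3. What the four categories mean is not stated.
- **Outcome (3.5.4).** "Change in 4-point Likert scale for edema at 24 h, 48 h and 72 h" is listed below the primary and secondary end-points, with no condition on the baseline score.
- **Analysis (3.6).** "The independent-samples Student's *t*-test and Mann-Whitney *U* test will be used as indicated to compare between groups". No baseline adjustment, stratification, subset or responder definition is given for this outcome, and no analysis population is named.

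The design (3.1) is "Randomized clinical trial with factorial 2x2 design, 2 treatment arms, and 4 groups (n=20 each"), which gives 40 v 40 for each factorial comparison. Allocation uses blocks of 4, with no stratification by edema mentioned.

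**The concern.** A patient can enter with, for example, jugular venous distension and pulmonary congestion on the radiograph and no edema. If the lowest category means no edema, that patient's change can only be zero or a worsening. The benefit that the outcome is meant to detect lies outside the scale.

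Such patients add mostly zeros to both groups. They pull the group means together and, when the other patients improve on average, they also add variance. With 40 per group there is little power to spare. A null edema result could then be read as no decongestive benefit when part of the cause is the measuring scale. This differs from the choice between an ordered and an unordered test, because the floor remains under either.

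**Working it through.** The plan gives no power, effect size or SD for this outcome, so there is no figure to reproduce. From the documents come n = 40 v 40 (3.1: 2 × 20 per side) and the two-sided 0.05 level (3.6). Everything else below is assumed.

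**1. Can a patient enter without edema?** Yes. Of the 6 pairs of listed signs, 3 lack edema: ascites + jugular distension, ascites + pulmonary congestion, and jugular distension + pulmonary congestion. Of the 11 combinations of two or more signs, 4 lack it. These counts show what entry allows, not how often it happens.

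**2. Dilution by formula.** Let f be the share at the floor, with zero change in both groups. Among the other patients assume a difference δ = 0.5 points, SD 0.8 and control mean change −1.0 (so −1.5 when treated).

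- Diluted difference = (1 − f)δ
- Variance in a group with mean change m = (1 − f)·0.8² + f(1 − f)m²
- Power ≈ Φ(difference / (SD·√(2/n)) − 1.96)

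At f = 20%:

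- Difference: 0.8 × 0.5 = 0.40.
- Variances: 0.512 + 0.16 × 1.00 = 0.672 and 0.512 + 0.16 × 2.25 = 0.872. The mean is 0.772, so SD = 0.879.
- All patients: 0.40 / (0.879 × √(2/40)) = 2.04, giving power of 53%.
- Only patients above the floor, n = 32 per group: 0.50 / (0.8 × √(2/32)) = 2.50, giving power of 71%.

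| Floor share | All patients | Above floor only |
|---|---|---|
| 0% | 80% | 80% |
| 10% | 66% | 76% |
| 20% | 53% | 71% |
| 30% | 42% | 65% |
| 40% | 33% | 58% |

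The restricted column also falls, because patients at the floor carry no information on improvement. Only the gap between the columns can be recovered by restriction.

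**3. Simulation with the Mann-Whitney test.** Assumed: patients with edema start at grade 1/2/3 in 35/40/25%, and each grade clears with probability 0.45 v 0.70.

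| Floor share | Change, all patients | Change, above floor only | Gap |
|---|---|---|---|
| 5% | 68% | 72% | 4 points |
| 10% | 60% | 68% | 8 points |
| 20% | 47% | 63% | 16 points |

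Repeated runs differ by a point or two. With a modest effect (0.45 v 0.55) and a 20% floor the figures are 12% v 16%, and power is only about 19% even with nobody at the floor.

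**4. Type I error.** In a similar simulation with equal clearance (0.40) in both groups and floor shares of 0 to 40%, rejection rates were 4.3% to 6.1%, consistent with 5%.

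**5. Using the baseline score in all patients.** Under the assumptions of step 3 at a 20% floor, comparing the follow-up score stratified by or adjusted for baseline gives about 77 to 80% power, against 63% for restriction and 47% for unadjusted change. Part of this gain does not come from the floor. In the assumed model, patients with more edema have more to lose, so conditioning on baseline also removes variance among them.

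**The case against.** The case for leaving the plan alone has real substance.

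- **The floor is inferred.** The category definitions are not in the documents. That the lowest means no edema is the natural reading, but it is an assumption. This stands.
- **The share is unknown.** If few patients lack edema, little is lost. This stands. A reader might take 4 of 11 (36%) as an estimate of that share. The documents do not support this: the list of signs is open-ended, and combinations are not equally common among patients.
- **The plan does not prescribe the weak analysis in so many words.** A reader might infer that 3.6 orders a comparison of all randomized patients regardless of baseline. It names no population. Scoring change in everyone is the fair default reading of that silence, not a stated rule.
- **The effect size matters.** A reader might conclude that a real effect on edema would probably be missed because of the floor. That does not follow. With a modest effect the trial is too small for this outcome whatever is done about the floor.
- **Restriction has a cost.** It changes the target population and moves new edema out of the main comparison. This stands, and it is why a baseline-adjusted analysis of everyone is preferable.
- **The consequence is low.** Sodium excretion, urine output, body weight and NT-proBNP also reflect decongestion and do not have this floor.

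What survives is that the plan collects a baseline score that would recover power and then does not say that it will be used.

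**Conclusion.** The point holds as a loss of sensitivity in one exploratory outcome. Entry permits patients without edema, the outcome is change, and the stated tests ignore where each patient started.

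The size cannot be fixed from the documents. The loss of 4, 8 or 16 points of power at floor shares of 5%, 10% or 20% rests on three assumptions: the lowest category means no edema, patients there stay there in both groups, and the effect in the others is fairly large. With the modest effect the loss at a 20% floor is about 4 points (12% v 16%).

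Two stronger conclusions are not supported. The comparison is not biased, because baseline edema precedes randomized treatment, and the false-positive rate is not raised. Nor does the point touch the sodium, potassium or secondary end-points. Priority is minor.

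**What to change.** In 3.4 or 3.5.4, state what each of the four edema categories means.

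In 3.5.4 and 3.6, state that the edema score at 24, 48 and 72 h is compared between groups in all patients, stratified by or adjusted for the score at randomization. A van Elteren test with the baseline category as stratum, or an ordinal model with baseline score as covariate, would do. Either keeps every patient and lets worsening from no edema count.

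As supportive results, report change among patients whose baseline score is above the lowest category, and new edema in the remaining patients as a count per group. The first is a subset fixed before treatment, so that comparison stays randomized. Show the baseline distribution of the score by group.

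The cost is a few sentences and slightly more analysis work. No new data are needed.
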